## SCALE-UP Utah II: Community-Academic Partnership to Address COVID-19 Text

Messaging Study

9/5/2024

NCT05533918

The primary hypotheses for the Smartphone study were main effects for delivery mechanism (Chatbot > TM), main effects for PN (PN > No PN), and main effects for message frequency (10-day > 30-day). For the non-Smartphone study, the primary hypotheses were main effects for PN (PN > No PN) and main effects for message frequency (10-day > 30-day). These hypotheses were adjusted for multiple comparisons using the Bonferroni method at an alpha of .0167 for the Smartphone study to account for three coprimary comparisons, and .0250 for the non-Smartphone study to account for two coprimary comparisons.

Separate analyses were conducted for the Smartphone study and the non-Smartphone study. Log-binomial models were used to regress *Reach-Accept Testing* upon each of the three main effects in the Smartphone study, i.e. Chatbot (vs. TM), PN (vs. No PN), and outreach frequency (10 vs. 30 days); and two main effects in the non-Smartphone study, i.e. PN (vs. No PN) and outreach frequency (10 vs. 30 days). The log-binomial models included covariates to adjust for randomization stratification variables (rural vs. urban, CHC, randomization arm in our previous SCALE-UP I trial) and a categorical variable reflecting the calendar month when the participant received the first intervention message. Adjusted risk ratios (aRR) and confidence intervals were reported for each main effect. In preliminary analyses reported in the Online Supplement, the pairwise and 3-way interactions between the main effects were added to the log-binomial models described

above in order to assess for any effect modifications across interventions, but these analyses did not support the inclusion of the interactions.

We preliminarily estimated a model specification including the pairwise and 3-way interactions between the main effects and the smartphone ownership indicator in order to assess for any synergistic and/or antagonistic effect modifications across interventions. We have conducted these analyses for the primary outcome (Reach-Accept Testing) for both the smartphone and non-smartphone groups. In both analyses, the estimated coefficients on all interaction terms were not statistically significant at the 5% level. We have conducted an omnibus test (using the car::linearHypothesis function in R) and found that in each case, these coefficients were jointly not statistically significant.

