Throughout the course of the study, on a quarterly basis, the study team will send identifiable patient data and study outcomes to project's sponsor, The National Institutes of Health. The identifiable information being transferred will include the CDE portion of the survey. This process will be detailed and approved through data transfer agreements involving the community health centers, the Association for Utah Community Health, The University of Utah Office of Sponsored Projects, The University of Utah IRB, and Duke University, which is housing the data for the National Institutes of Health.

● Yes ○ No		• .		·	ŕ	
If no list the n	rocedures that are n	erformed for res	search nurnoses onl	v (non-standard o	r non-stand	1:

7. Are all procedures for research purposes only (non-standard or non-standard of care procedures)?

If no, list the procedures that are performed for research purposes only (non-standard or non-standard of care procedures):

8. Is there a safety monitoring plan for this study?

Yes No

9. Provide a summary of the statistical methods, data analysis, or data interpretation planned for this study. Factors for determining the proposed sample size (e.g., power) should be stated.

We will conduct two randomized clinical trials: RCT 1 includes participants who affirm they have a smart phone and RCT 2 includes all other participants. We will perform two categories of statistical analyses: 1) Comparing the main effects of TM vs. CA (RCT 1), main effects of RPN vs. no PN (RCT 1 and 2 combined), interaction effects (RCT 1), and follow-up pairwise comparisons of the study arms (RCT 1 and 2); and 2) Evaluating predictors of outcomes and moderators of intervention effects (RCT 1 and 2).

Primary Analyses of Testing for TM vs. CA and no PN vs. RPN. Alpha will be set at 0.0167 to maintain a family-wise error rate of 0.05 across the three primary hypotheses comparing treatment arms. We will apply generalized estimating equations to implement a repeated measures logistic regression to relate the probability of receiving a COVID-19 test within a shorter time frame to the randomized treatment group. Robust sandwich variance estimates will be utilized to account for dependencies between potential repeated observations on each subject (i.e. several potential time-intervals post-randomization where patients might test).

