Predictors of outcomes and moderators of intervention effects. Multilevel generalized linear mixed models will investigate the association between patient, provider, and CHC/clinic level predictor variables with implementation outcomes for each intervention. We will test for patient characteristics and contextual pandemic factors as outcome moderators by fitting an interaction term of each moderator by intervention.

Statistical Power. The participating CHCs have 43,325 patients with a clinical encounter in the past three years. In SCALE-UP Utah, 15% of patients have opted out of receiving text messages and will not be included in SCALE UP II. Based on data from SCALE-UP Utah and prior research, we anticipate ~20% opt outs, leaving a total of ~29,500

patients for randomization to the six study arms. We have satisfactory power for detecting feasible CA vs TM; and RPN vs No PN differences on our primary outcome of *Recurrent-Testing*.

IRB_00150669

Created: 1/10/2022 7:14 AM IRB_00150669

- Request for Waiver of Consent

PI: [name] [name]

Submitted: 3/21/2022

Title: SCALE UP Utah II: Community-Academic Partnership to Address COVID-19 Testing and Vaccination Among Utah Community Health Centers

Request for Waiver or Alteration of Consent -

	Date Created	Type of Request	Purpose of Waiver Request
View	2/25/2022	Waiver of Informed Consent	The purpose of this waiver is to review EHR patient data at participating CHCs and linked USIIS vaccination data, using that data to establish cohort selection for research intervention and randomizing selected patients to research interventions without the patient's consent.
View	2/25/2022	Waiver of Informed Consent	The purpose of this waiver is for the use of EHR and USIIS data post-intervention implementation to analyze which patients, randomized to each intervention, were ultimately tested and/or vaccinated for COVID-19.

PI: [name] [name] Submitted: 3/21/2022

Title: SCALE UP Utah II: Community-Academic Partnership to Address COVID-19 Testing and Vaccination Among Utah Community

Health Centers

Request for Waiver or Alteration of Consent

1. Purpose of the Waiver Request:

The purpose of this waiver is to review EHR patient data at participating CHCs and linked USIIS vaccination data, using that data to establish cohort selection for research intervention, and randomizing selected patients to research interventions without the patient's consent.

2. Type of Request:

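### Fixed Bonferroni thresholds for the coprimary effects are valid but give up a little power that Holm's step-down would recover at the same family-wise error

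*SAP*

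**What the plan says.** The opening paragraph of the SAP names three coprimary main effects for the Smartphone study (chatbot against text messaging, patient navigation against none, 10-day against 30-day messaging) and two for the non-Smartphone study (navigation and frequency). The method is single-step Bonferroni: "These hypotheses were adjusted for multiple comparisons using the Bonferroni method at an alpha of .0167 for the Smartphone study", and .0250 for the two tests in the other study.

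The Protocol (Study Information, item 9, primary analyses) gives the aim: "Alpha will be set at 0.0167 to maintain a family-wise error rate of 0.05 across the three primary hypotheses comparing treatment arms".

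On estimates, the SAP says: "Adjusted risk ratios (aRR) and confidence intervals were reported for each main effect". It does not give the confidence level.

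On power, the Protocol's Statistical Power paragraph says only: "We have satisfactory power for detecting feasible CA vs TM; and RPN vs No PN differences on our primary outcome". It gives no event rate, effect size or power value. It expects about 29,500 patients but does not split them between the two studies.

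Neither document mentions a step-down or gatekeeping procedure, or a reason for preferring the single-step one.

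**The concern.** Under single-step Bonferroni each test must meet the same threshold whatever the other tests show. The aim of 0.05 does not require this. Once the smallest p-value in a family has passed, the remaining hypotheses can be tested at a less strict level without raising the family-wise error above 0.05.

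Two examples for the Smartphone study:
- The smallest p-value is below .0167 and the next is .02. Bonferroni calls the second effect not shown; Holm rejects it, since .02 is below .0250.
- The two smaller p-values pass and the largest is .04. Bonferroni calls the third effect not shown; Holm rejects it, since .04 is below .0500.

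The chatbot, the navigator and the message frequency can each be adopted separately, so a component declared unproven only because of the testing rule is a lost conclusion.

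**Working it through.** **1. The plan's figures.** 0.05/3 = .01667, stated as .0167. 0.05/2 = .0250. Both reproduce. With all nulls true and independent tests, the family-wise error is 1 − (1 − 0.05/3)³ = .0492 and 1 − (1 − .025)² = .0494.

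**2. Holm's rule.** Order the p-values from smallest to largest, compare them with .0167, .0250, .0500 (three tests) or .0250, .0500 (two tests), and stop at the first failure.

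- *It keeps every Bonferroni rejection.* No Holm threshold lies below the Bonferroni one.
- *It holds 0.05.* Let m of the hypotheses be true nulls. When Holm first rejects one of them, at least m hypotheses are still in play, so the threshold is at most 0.05/m. The chance that any of m true nulls has p ≤ 0.05/m is at most m × 0.05/m = 0.05. This needs no independence.

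A simulation (1,000,000 replicates per scenario) found no case in which Bonferroni rejected and Holm did not. With all nulls true the family-wise error was .0489 (three tests) and .0494 (two), the same under both rules. With 80% power for the real effects, Holm's family-wise error was at most .0458 (three tests) and .0454 (two).

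**3. Size of the gain.** Assumptions, none from the documents: two-sided tests, independent statistics (as in a balanced factorial), equal power for every real effect, and Bonferroni power from 50% to 95%.

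For three tests, let a, b and c be the power of a real effect at .0167, .0250 and .0500. Let u1, u2 and v1, v2 be the rejection probabilities of the other two tests at .0167 and .0250. Holm's power is

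a + (b − a)[1 − (1 − u1)(1 − v1)] + (c − b)[u2·v2 − (u2 − u1)(v2 − v1)].

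At a = .800 the mean z is 2.394 + 0.842 = 3.236, which gives b = .8399 and c = .8990.

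- Three real: .800 + .0399 × .960 + .0590 × .7039 = .880.
- Two real (the null test has .0167 and .0250): .800 + .0399 × .8033 + .0590 × .0207 = .833.
- One real: .800 + .0399 × .0331 + .0590 × .0006 = .801.

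For two tests with both effects real, let b and c be the power at .0250 and .0500. Holm's power is b + (c − b)b. At b = .800, c = .8693, so .800 + .0693 × .800 = .855.

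Power per real effect under Holm:

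| Bonferroni power | 3 tests, 3 real | 3 tests, 2 real | 3 tests, 1 real | 2 tests, 2 real |
|---|---|---|---|---|
| 50% | 57.9% | 53.2% | 50.2% | 55.5% |
| 80% | 88.0% | 83.3% | 80.1% | 85.5% |
| 90% | 95.2% | 92.3% | 90.1% | 93.7% |
| 95% | 98.0% | 96.4% | 95.0% | 97.2% |

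Chance of showing every effect when all are real (Bonferroni → Holm):

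| Bonferroni power | Three of three | Two of two |
|---|---|---|
| 50% | 12.5% → 27.6% | 25.0% → 36.1% |
| 80% | 51.2% → 71.7% | 64.0% → 75.1% |
| 90% | 72.9% → 87.3% | 81.0% → 88.4% |
| 95% | 85.7% → 94.4% | 90.3% → 94.6% |

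Where the simulation covers the same cells, it agrees to about 0.1 point. The chance of at least one rejection is identical under both rules.

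**The case against.** **No error is present.** Bonferroni delivers the error rate that the Protocol asks for. A reader might infer that the multiplicity plan is defective or inflates type I error. It does neither: there is no bias, and the choice costs only efficiency. This stands and sets the grade.

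**The size is conditional.** A reader might take the 80% to 88% contrast as the loss in this trial. The documents do not support that, because 88% needs three real effects and the 80% is assumed. With one real effect of three there is almost no gain, and each true null is rejected more often (about 1.7% becomes 2.4% at 80% power, still within the 0.05 limit). Power near 100% also leaves nothing to recover. For illustration, with 20,000 patients split evenly and 10% acceptance in the comparison group (both assumed), power at .0167 is 46.5% for a risk ratio of 1.1 and 98.3% for 1.2. This stands.

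**No named hypothesis is lost.** Holm helps the second- or third-smallest p-value, whichever hypothesis that is, and only when the smaller ones pass. The non-Smartphone study has no third test. The p-values of .02 and .04 above are examples, not results. This stands.

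**A change may be post hoc.** The SAP is dated 9/5/2024, is written in the past tense and already reports the interaction tests as not significant. A reader might infer that Holm should simply replace Bonferroni. If the main-effect results are known, that would loosen thresholds after the fact. The documents do not settle whether they were known, so the remedy must depend on it.

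**Bonferroni intervals match Bonferroni tests.** Holm has no equally simple matching intervals. This is a real but small cost, since the Bonferroni intervals can be kept as conservative ones.

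**Conclusion.** The point holds as a minor loss of efficiency. For the stated aim of 0.05, Holm is at least as powerful as the declared rule under any dependence, and this is true however the families are finally drawn. The gain is 3 to 8 points per effect when all three are real, 1 to 3 when two of three are, at most 0.2 when one is, and 2 to 6 for two tests with both effects real. These sizes rest on independent, equally powered two-sided tests and on an assumed 50% to 95% power. Only the error control and the retention of Bonferroni rejections are free of those assumptions. Nothing here shows that a conclusion of this trial was in fact lost.

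**What to change.** - **If the main-effect results are documented as unseen:** in the SAP and in item 9 of the Protocol, replace the fixed thresholds with Holm's step-down at family-wise 0.05 within each study (.0167, .0250, .0500 for the Smartphone study; .0250, .0500 for the non-Smartphone study). Report Holm-adjusted p-values.
- **If they have been seen, or this cannot be documented:** keep the Bonferroni conclusions as confirmatory and add the Holm-adjusted p-values for the five tests, labelled as a sensitivity analysis. Use Holm as the primary rule in a successor plan.
- **In both cases:** report Bonferroni intervals at 98.33% (1 − 0.05/3) and 97.5% (1 − 0.05/2) and state the level.

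The cost is a sentence or two in each document and no new data. Under Holm, an interval of this width can include 1 for an effect that is rejected; a note beside the results should say so.

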- c. **Patient Navigation (PN):** phone call from a community health worker to help address hesitancy and access barriers, and to offer at-home rapid test kits. Two types of PN will be tested: **Request PN** (RPN) will contact only those patients who reply YES to a TM/CA message. No PN will have no contact from a patient navigator.

Prior to randomization, patients will be triaged into one of two studies based on self-reported ownership of a smart phone with internet access.

The primary outcome, Testing, captures whether patients actually test with the mailed at-home test kit.

Secondary outcomes include: *Time-To-Vaccine* (time-to-event outcome) as well as several implementation outcomes including *Reach-Engage Testing* (proportion of patients that reply to an offer to receive an at-home rapid test kit) and *Reach-Accept Testing* (proportion of patients that accept an offer to receive an at-home test kit). A similar set of implementation outcomes will be measured for vaccination (i.e., *Reach-Engage Vaccine* and *Reach-Accept Vaccine*).

8. Background and Introduction:

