The process for this matched collection is as follows... Participating Community Health Centers will send USIIS a list of patients participating in SCALE UP. These records will include patient identifiers such as name, DOB, address, primary clinic, and MRN. Community Health Centers routinely send patient information to USIIS. This transfer of data is routine clinical practice and covered through DUAs between the clinics and USIIS. USIIS will then perform a match between the lists from the CHCs and their vaccination records. USIIS will then send the University of Utah the matched data sets. These records will include name, DOB, address, primary clinic, MRN, and COVID-19 vaccination administration details. This transfer will take place over a HIPPA compliant platform and be stored securely at the Center for High Performance Computing. These data matches and transfer from USIIS to the SCALE UP team will occur as frequently as every two weeks to ensure that researchers are using the most up to date vaccination records for patients.

Step Three:

Cohort Selection & Randomization

Once the data are securely housed at the Center for High Performance Computing, the study team will determine cohort building criteria. Cohort selection will be based on EHR data considering factors such as age, race/ethnicity, language, relevant medical comorbidities, and residence in hotspot areas. These selection criteria are consistent with recommendations from UDOH and the CDC.

Once the cohort selection criteria are determined, patients are assigned between the two study designs based on their answer to the smart phone screener question. Once triaged to each study, patients are then randomized between the various arms and conditions within each study.

Step Four:

Implementation

Text Messaging Only Study

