Patients assigned to the Text Message study will receive HIPPA-compliant bidirectional texts, which is a communication method routinely used by the CHCs, to patients in high-risk cohorts. Text messages will be designed by the research team and sent using a HIPPA compliant text messaging service. The text messaging service will retrieve the patient cohort from the study database to send the TMs to the patients. The text messages will appear to the patients as having originated from their CHC. As part of their general CHC care, patients have agreed to be contacted by their CHC and text message communication is one of those established contact methods. Text messages will be repeated either every 10 days or 30 days, to continuously screen for COVID-19 testing and vaccination eligibility and to provide updates. Every text message will include the option to reply STOP to cease receiving text messages at any time.

Text messages will include a brief message regarding COVID-19 testing and/or vaccine information. The content of the text messages will be the same across the three different patient navigation conditions.

Patients in the TM only (No PN) condition who reply "yes" will receive additional messages with a recommendation to be tested, testing locations/hours/phone, and/or have the ability to request a free at-home test be sent to their home on behalf of their CHC.

Patients assigned to TM+RPN who reply "yes" will receive a call from a Patient Navigator. Patient Navigators will talk to patients about free at-home testing and patients will have the option to request a free at-home test sent to the patient on behalf of their CHC. The duration of patient navigator involvement will vary from patient to patient, depending on the complexity of the case. If a patient declines PN they will no longer receive PN intervention.

Conversational Agent/Text Message Study

Patients assigned to the CA/TM Study will be randomized between receiving access to a Conversational Agent (CA) or the same bi-directional text message intervention as the Text Message Study (TM). Patients in both groups (CA and TM) will then be randomized between two arms of patient navigation, No PN or RPN. Therefore, in the CA/TM study, there are four different groups of participants: CA only, CA+RPN, TM only, and TM+RPN. The two arms of patient navigation are the same as in the TM Only Study.

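### The primary models adjust for first-message month, which is fixed after randomisation and missing for any randomised patient without a message; the effect on the risk ratio is unknown and may be negligible

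*SAP*

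**What the plan says.** The SAP's paragraph on the log-binomial models lists two kinds of covariate. The first is the stratification factors: rural or urban location, health center, and arm in the preceding SCALE-UP I trial. The second, entered as categories, is the "calendar month when the participant received the first intervention message". Month of randomisation is not in the list. On the results, the SAP says: "Adjusted risk ratios (aRR) and confidence intervals were reported for each main effect".

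The Protocol (section 4, Study Information, question 6) gives the order of events. Step Three covers the smartphone screener and then allocation: "Once triaged to each study, patients are then randomized between the various arms and conditions within each study". Messaging belongs to Step Four, Implementation, and its form depends on the arm. Patients in the Conversational Agent/Text Message Study "will be randomized between receiving access to a Conversational Agent (CA) or the same bi-directional text message intervention".

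The outcome in the SAP models is Reach-Accept Testing, which the Protocol (Study Purposes and Objectives) defines as the "proportion of patients that accept an offer to receive an at-home test kit".

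**The concern.** A covariate in a randomised comparison should be fixed before allocation, or at least be incapable of depending on it. The month of the first intervention message is set after allocation, by a process that belongs to the intervention. Two problems could follow.

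- **Missing values.** A randomised patient with no first message has no month. Standard regression software deletes that record, so the analysis moves from everyone randomised to those reached. That matters for a reach outcome, because a patient who never got the offer is a non-acceptor, and failure to reach is part of what a comparison of delivery methods should count.
- **Adjusting for a consequence of allocation.** If one arm's first messages went out later and acceptance changed over the pandemic, adjusting for message month removes the part of the effect that acts through timing.

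The SAP settles neither problem. It does not define receipt (sent, delivered or opened), does not say what happens to a record without a month, and states no analysis set.

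**Working it through.** **Inputs from the documents**
- Source population 43,325; 15% prior opt-out; about 20% anticipated opt-out; about 29,500 for randomisation (Protocol, section 4, question 9, Statistical Power).
- Order of events and type of message: Steps Three and Four, as above.
- Share never reached, and first-message timing by arm: not given. Every value below for these is an assumption.

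**1. The plan's own number.** 43,325 × (1 − 0.15) × (1 − 0.20) = 29,461, which agrees with about 29,500. It is used here only to put a scale on possible losses.

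**2. Patients lost under case deletion.** With never-reached share u, the loss is 29,500 × u:
- u = 1%: 295
- u = 5%: 1,475
- u = 10%: 2,950

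**3. Effect on acceptance proportions.** Unreached patients all have outcome 0, so removing them multiplies the proportion by 1/(1 − u):
- u = 1%: 1.010
- u = 10%: 1.111

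**4. Effect on the risk ratio.** Let q1 and q0 be the shares reached in the two arms, and r1 and r0 the acceptance among those reached. The all-randomised ratio is (q1 × r1)/(q0 × r0), and the reached-only ratio is r1/r0. Reached-only divided by all-randomised is therefore q0/q1, before covariate adjustment:
- equal reach: 1.000
- 98% vs 96%: 0.98/0.96 = 1.021
- 98% vs 93%: 0.98/0.93 = 1.054

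**5. Effect through timing, with no missing data.** Assume that acceptance falls by a factor exp(−0.25) = 0.779 per month, that a share s of one arm gets its first message a month late, and that the arms do not otherwise differ. The total effect of allocation is then 1 − s + s × 0.779:
- s = 0.25: 0.945
- s = 0.50: 0.889

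Adjustment for message month should return 1.000 in both cases, because acceptance here depends on that month alone. A simulation of 400,000 patients gave the following for randomisation-month against message-month adjustment:
- s = 0.25: 0.948 against 1.005
- s = 0.50: 0.878 against 0.986

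With no delay, both adjustments gave 1.011 where 1.000 is correct, so differences of about 0.01 are simulation noise.

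**6. A separate category for no message.** This would not rescue the covariate. The category contains no acceptors, so its log-binomial coefficient has no finite estimate.

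**The case against.** The strongest reply is that the covariate may be complete and nearly the same as month of randomisation. Step Four describes a send-driven system: the messaging service takes the cohort from the study database and texts it. If receipt means first send, the month exists for everyone messaged, whether or not they read or answered.

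Several safeguards also limit unreached patients. Eligibility requires a working cellphone. The power section takes opt-outs off before it arrives at the number for randomisation. A screener text comes before allocation, so many refusals should occur there. Screener non-responders are kept in the Text Message Only study, but silence is not proof of non-delivery.

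Dependence on arm is not shown either. The frequency factor concerns repeats: "Text messages will be repeated either every 10 days or 30 days". Nothing says that it changes the first message. Navigation follows a patient's reply, so it cannot affect the first message. The conversational agent and the text service are separate platforms, which makes a difference in delivery or logging possible, but none is reported.

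Month of first contact is also a defensible calendar marker. If patients were randomised in batches and messaged in waves, it describes conditions at the time of the offer better than the randomisation date does.

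All of this stands, and it bears on size. It does not remove the gap in the SAP: the variable is fixed after allocation, receipt is undefined, and a missing month has no rule.

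A reader might infer that the reported analysis excluded unreached patients, or that its risk ratios are biased. The documents support neither: no deletion and no imbalance is described. Nor can the anticipated 20% opt-out be read as the unreached share, since the plan removes it before randomisation.

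**Conclusion.** The primary models use a covariate that is fixed after randomisation and has no value for a randomised patient without a first message. Whether this changes anything depends on facts that the documents do not give.

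- If receipt means sent and everyone was messaged promptly, the effect is negligible.
- If some patients have no month, a standard fit drops them. Acceptance proportions rise, but the risk ratio does not move when reach is equal across arms.
- If reach differs by arm, the risk ratio shifts by the ratio of the reached shares: about 2% for an assumed 98% vs 96%, and about 5% for 98% vs 93%.
- If first-message timing differs by arm, adjustment can hide part of the effect even with complete data. The figures for this case rest on assumed delays and an assumed decline in acceptance, and show the direction only.

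This is a minor point. Adjusting for calendar time is sound; only the anchor date and the handling of patients without a message are in question. The change is worth making because it costs little and closes off a bias that the documents leave open.

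**What to change.** 1. In the primary models, replace the covariate with calendar month of randomisation. If patients were randomised in batches and messaged in waves, use instead the scheduled first-send month, provided that it was set independently of arm.
2. State that every randomised patient stays in the model, and count those without a message as non-acceptors.
3. Define receipt as sent, delivered or opened, and report by arm the number of randomised patients with no first-message date.
4. Keep the present model as a sensitivity analysis.

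The SAP describes its analyses in the past tense, so the cost is a short text change and a re-run of the models. Control of calendar time may be slightly looser if messaging lagged randomisation. The change also assumes that the randomisation date (or the scheduled send date) is stored in the study database, which the documents do not state. If the current covariate proves to be complete and close to month of randomisation, the two sets of results should agree, and reporting both will show that.
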